### **5.6 Visit 5 (12 days +/- 7 days)**

Patients in the PAE group and the Control group will have the following:

- Physical exam including vital signs, weight, and genitourinary evaluation
- Blood and urine laboratory evaluations as at baseline
- Concomitant medications
- Adverse events
- Urinary catheter removal

Cystoscopy and proctoscopy will be performed: 1) if medically indicated, especially if there is pain out of proportion to that which is expected, 2) in all cases of bleeding per rectum, and 3) in cases of hematuria beyond that which is reasonably expected following prostatectomy.**5.7 Visits 6, 7, 8, 9 (3, 6, 9, and 12 months ± 2 weeks for each visit post RALRP)**

Patients in the PAE group will have the following assessments performed:

- Physical exam including vital signs, weight, and genitourinary evaluation
- Prostate Specific Antigen (PSA)
- Expanded Prostate Cancer Index Composite (EPIC) questionnaire
- International Index of Erectile Function (IIEF) questionnaire
- Pad weight test
- Concomitant medications
- Adverse events

Cystoscopy and proctoscopy will be performed: 1) if medically indicated, especially if there is pain out of proportion to that which is expected, 2) in all cases of bleeding per rectum, and 3) in cases of hematuria beyond that which is reasonably expected following prostatectomy.

Patients in the Control group will have the following assessments performed:

- Physical exam including vital signs, weight, and genitourinary evaluation
- Prostate Specific Antigen (PSA)
- Expanded Prostate Cancer Index Composite (EPIC) questionnaire
- International Index of Erectile Function (IIEF) questionnaire
- Pad weight test
- Concomitant medications
- Adverse events

### **5.8 Annual Long-Term Follow-Up**

After the 12 month visit, patients in both groups will continue to be followed according to the standard follow-up protocol for the treating institution.

## **6 Withdrawal of Patients**

Patients will be informed that they have the right to withdraw from the study at any time for any reason, without prejudice to their medical care. The Investigator also has the right to withdraw patients from the study for any of the following reasons:

- Adverse events
- Refusal of treatment
- Patient request
- Inability to complete study procedures
- Lost to follow up
- Noncompliance with study requirements

If a patient is withdrawn or discontinued from the study, the reason for withdrawal from the study will be recorded in the source documents and on the Study Termination CRF. All patients withdrawn from the study will be encouraged to complete, if possible, all clinical evaluations scheduled for the 12 month visit. All adverse events should be followed as described in Section 7. Patients who are withdrawn from the study for any reason will not be replaced.

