#### ***9.5.2.8 Return to Continence***

An analysis of return to continence post RALRP will be performed using the pad weight test. Patients will be classified as being continent if the weight of the pad increase is insignificant; mild incontinence if the weight of pad increases by <400 grams over 24 hours and as incontinent if the weight of the pad increases by  $\geq 400$  grams over 24 hours. The pad weight test will be performed at the following post-RALRP timepoints: 12 days (if urinary catheter is removed), 3 months, 6 months, 9 months, and 12 months. The proportion of continent patients will be calculated for each treatment group at each timepoint. Treatments will be compared using an exact binomial sign test.

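### Section 6 lets the investigator withdraw men from the study for adverse events, inability or noncompliance without separating stopping a procedure from leaving follow-up, so outcome data after RALRP can be lost selectively.

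*Combined protocol and SAP*

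**What the plan says.** Section 6 of the combined protocol and SAP first protects the patient's own right to leave. It then adds: "The Investigator also has the right to withdraw patients from the study for any of the following reasons". Adverse events head the list, which also contains "Inability to complete study procedures" and "Noncompliance with study requirements". The withdrawal is from the study as a whole. The section has no separate category for a man who does not have, or does not complete, a procedure but remains under observation. Withdrawn men are not replaced.

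Two safeguards follow in the same section. On evaluations: "All patients withdrawn from the study will be encouraged to complete, if possible, all clinical evaluations scheduled for the 12 month visit". On safety: "All adverse events should be followed as described in Section 7". Section 7.2 requires follow-up to a final outcome only for events judged related to study treatment. Sections 7.1 and 7.2 also ask for all events to be recorded through the 12-month follow-up period, with assessment at each visit.

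The follow-up in question is Visit 5 (about 12 days after RALRP) and Visits 6 to 9 (months 3, 6, 9 and 12), described in sections 5.6 and 5.7. Section 9.5.2.8 uses these visits for continence: "The proportion of continent patients will be calculated for each treatment group at each timepoint". Section 9.5.2.9 does the same for the IIEF subscales, and section 9.5.2.7 assesses biochemical recurrence at Visit 9.

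**The concern.** PAE and RALRP are each performed once. After RALRP a man receives no further study treatment, and Visits 5 to 9 consist of examinations, laboratory tests, questionnaires, pad weights, medication and event recording, and catheter removal. Withdrawing him at that stage for an adverse event spares him no study treatment. It only ends his scheduled observation.

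The grounds for removal overlap with what is being measured. Continence, erectile function, recurrence and adverse events are all study outcomes, so a man may be withdrawn because of his outcome or something closely linked to it. The study is non-randomized and describes no blinding, and one group has an extra procedure, so the decision would be made with the treatment group known. If the men who leave have done worse, those who remain make their group look better than it is. With ten pairs, no replacement and no rule in section 9 for missing values or broken pairs, one or two such losses would be visible in the results.

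**Working it through.** **No plan figure to reproduce.** Section 9.2 says no formal sample size calculation was made, and the documents give no dropout rate. The sums below are illustrations. The number of withdrawals and the outcome rates are assumed.

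**Inputs.** Ten PAE men and ten controls, matched 1:1 (sections 4 and 9.2). Paired t-tests for continuous outcomes and exact binomial sign tests for binary ones (section 9.5.2). No replacement (section 6).

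**1. What each safeguard covers after a post-RALRP withdrawal.**

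| Data | Scheduled | Covered by section 6 after withdrawal |
|---|---|---|
| Continence, IIEF, PSA at months 3, 6, 9 | Visits 6 to 8 | Nothing stated |
| Continence, IIEF, PSA at month 12 | Visit 9 | Encouraged, if possible; date not stated |
| Known treatment-related adverse events | All visits | Followed to a final outcome (section 7.2) |
| Other or new adverse events | All visits | To be recorded for 12 months, but assessed at visits the withdrawn man no longer has; unclear |
| EBL, POD1 hemoglobin and hematocrit, transfusion, duration, margins | Around RALRP | Already collected |

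**2. Shift in a proportion.** If k of 10 men are continent and one incontinent man leaves, the rate moves by k/9 − k/10 = k/90. If two leave, it moves by k/8 − k/10 = k/40. With k = 6:
- none leave: 6/10 = 60%
- one leaves: 6/9 = 66.7%, a shift of 6/90 = 6.7 points
- two leave: 6/8 = 75%, a shift of 6/40 = 15 points

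For an adverse outcome present in 3 of 10 men (30%), losing one or two of those three gives 2/9 = 22.2% or 1/8 = 12.5%.

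**3. Shift in a mean.** In simulated normal samples of ten, removing the worst one or two values improves the group mean by about 0.17 or 0.32 SD. This is the most unfavorable pattern for a score such as an IIEF subscale.

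**4. Precision.** The half-width of a paired 95% interval is t(0.975, n−1) × SD/√n.
- n = 10: t/√n = 0.715
- n = 8: t/√n = 0.836
- ratio: 0.836/0.715 = 1.17, about 17% wider at equal SD

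**5. Sign test.** Two-sided p ≤ 0.05 needs at least six discordant pairs, all in one direction: 2 × 0.5⁶ = 0.031, against 2 × 0.5⁵ = 0.0625 for five. Losing pairs makes six discordant pairs harder to reach.

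**The case against.** The clause is permissive. It gives the investigator a right and does not instruct anyone to remove a man for a complication or a missed pad test. Section 6 also contains two safeguards, so it would be wrong to treat the month-12 encouragement as the only one. A treatment-related complication would still be followed to its outcome under section 7.2. These points stand, and they limit the problem. They do not close it, because months 3, 6 and 9 are uncovered, month 12 is optional, and the recording of new events after withdrawal is unclear.

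Withdrawal also has a real function for a PAE man in the roughly ten weeks before RALRP, since he still has a procedure ahead. A reader might infer from section 6 that there is never anything left to stop. That is true only after RALRP.

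A reader might also infer that exit evaluations will be analyzed as Visit 9 data. The documents do not say so. Section 6 speaks of the evaluations scheduled for the 12-month visit, section 5.7 places that visit at month 12 ± 2 weeks, and a withdrawn man could simply be asked to return then. The timing is unstated, which is an ambiguity and not an established bias. If early values were counted as Visit 9, continence would tend to look worse, while selective departure would make it look better, so no net direction can be claimed.

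Finally, the post-12-month provision in section 5.8, that "patients in both groups will continue to be followed according to the standard follow-up protocol for the treating institution", does not repair the gap at months 3 to 9.

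**Conclusion.** The point holds in a limited form. Section 6 merges two different events, and after RALRP the merger can only cost outcome data. The exposure is in continence, IIEF, biochemical recurrence and late adverse events. A reader might infer that the primary comparison is at risk too. It is not: EBL is recorded during surgery, and the other perioperative outcomes cannot be altered by a withdrawal once RALRP and the associated stay are over.

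Under the assumed 6/10 continence, one or two selective withdrawals move the reported rate by 6.7 or 15 points, and two lost pairs widen a paired interval by about 17%. These sizes rest on assumed withdrawals, on the men who leave being those with poor outcomes, and, for the interval, on an unchanged SD. The documents give no basis for predicting how many men would be withdrawn. In a proof-of-concept study the matter warrants a wording change and does not invalidate the design.

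**What to change.** Reword section 6 to distinguish (a) not receiving or not completing PAE or RALRP from (b) leaving follow-up.

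- Limit (b) to the patient's withdrawal of consent, loss to follow-up or death.
- State that adverse events, inability to complete a procedure and noncompliance do not end follow-up. Consenting men then stay on the Visit 5 to 9 schedule for adverse events, PSA, IIEF, EPIC and pad weight, with institutional follow-up results used when they do not attend.
- Record a withdrawn man's 12-month evaluations under their actual date, and count them as Visit 9 only within month 12 ± 2 weeks.
- Visits 5 to 9 are timed from RALRP, so say from which date follow-up is counted for a man who has PAE but not RALRP. Section 9.3 would still leave him out of the analysis population; this rewording alone does not change that.

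None of this touches the clinical decision on whether a procedure goes ahead. The cost is protocol wording, one field on the Study Termination CRF and slightly more follow-up effort. Section 4.2 already has both groups followed after RALRP under the treating institution's standard protocol. The patient's own right to withdraw is unchanged.

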## 7 Adverse Events

### 7.1 Definitions

#### Adverse Event

An adverse event (AE) is any untoward medical occurrence in a patient or clinical investigation subject and does not necessarily have to have a causal relationship with the treatment. An AE therefore can be any unfavorable or unintended sign (including a clinically significant abnormal laboratory finding, for example), symptom or disease temporally associated with the use of a medicinal product or procedure, whether or not considered related to the product or procedure. A non-serious AE is any untoward medical occurrence that does not meet any of the criteria for an SAE as defined below.

Laboratory data are to be collected as stipulated in this protocol. Clinical syndromes associated with laboratory abnormalities are to be recorded as appropriate (eg, diabetes mellitus instead of hyperglycemia).

Patients should be instructed to report any AE that they experience to the Investigator or Study Coordinator. AEs will be assessed at each visit. AEs occurring during the clinical trial and the protocol-defined 12-month follow-up period should be recorded on the appropriate AE CRF. In order to capture the most potentially relevant safety information during this study, it is important that the Investigator records AE terms accurately and consistently throughout the study. Wherever possible, a specific disease or syndrome should be reported on the CRF rather than the associated individual signs and symptoms. If observed or reported signs or symptoms are not considered a component of a specific disease or syndrome by the Investigator they should be recorded as separate AEs on the CRF.

All adverse events will be assessed for severity, relationship to study treatment, subsequent treatment required for the adverse event, and outcome/resolution. This information will be recorded on the Adverse Event CRF pages.

Adverse events that might occur in this study include, but are not limited to:

- For cystoscopy and PAE:
  - Burning in the urethra, urinary infection, hematuria, pain
- For PAE:
  - Hematospermia, hemorrhage, injury to bladder, including bladder neck, ureteral orifice or trigone, impact on future fertility, vasospasm, rectorrhagia, inguinal hematoma, bladder/bladder neck ischemia and necrosis, bladder resection, allergic reaction to microspheres or contrast agent, radiation exposure, vascular perforation

### **Serious Adverse Event (SAE)**

A serious adverse event (SAE) is any adverse event, occurring at any dose and regardless of causality that:

- **Results in death.**
- **Is life-threatening**, where life-threatening means that the subject was at immediate risk of death from the reaction as it occurred (i.e., it does not include a reaction which hypothetically might have caused death had it occurred in a more severe form).
- **Requires in-patient hospitalization or prolongation of existing hospitalization.** Hospitalization admissions and/or surgical operations scheduled to occur during the study period, but planned prior to study entry are not considered AEs if the illness or disease existed before the subject was enrolled in the trial, provided that it did not deteriorate in an unexpected manner during the trial (e.g., surgery performed earlier than planned).
- **Results in persistent or significant disability/incapacity**, where disability is defined as a substantial disruption of a person's ability to conduct normal life functions.
- **Is a congenital anomaly/birth defect.**
- **Is an important medical event as defined by the Investigator.** An important medical event is an event that may not result in death, be life-threatening, or require hospitalization, but may be considered an SAE when, based upon appropriate medical judgment, it may jeopardize the patient or subject and may require medical or surgical intervention to prevent one of the outcomes listed in the definitions for SAEs. Examples of such medical events include allergic bronchospasm requiring intensive treatment in an emergency room or at home, blood dyscrasias or convulsions that do not result in inpatient hospitalization, or the development of drug dependency or drug abuse.

Clarification should be made between the terms "serious" and "severe" since they are not interchangeable. The term "severe" is often used to describe the intensity (severity) of a specific event (as in mild, moderate, or severe myocardial infarction); the event itself, however, may be of relatively minor medical significance (such as a severe headache). This is not the same as "serious," which is based on subject/event outcome or action criteria described above and are usually associated with events that pose a threat to a subject's life or functioning. A severe adverse event does not need to be considered serious. For example, persistent nausea of several hours duration may be considered severe nausea but not constitute a SAE, unless the patient would be admitted to the hospital or the event would meet any other of the criteria for seriousness. On the other hand, a stroke resulting in only a minor degree of disability may be considered mild, but would be defined as an SAE based on the above noted criteria. Seriousness (not severity) serves as a guide for defining regulatory reporting obligations.

Under this protocol, scheduled hospitalizations or elective surgical procedures will not be considered SAEs. Prolongation of a scheduled hospitalization will be considered an SAE as defined above. Complications associated with surgical procedures or study treatments resulting in one of the outcomes above are considered SAEs.

## **7.2 Adverse Event Reporting**

The Investigators are responsible for monitoring the safety of patients who have been enrolled in this study. All AEs considered to be related to study treatment will be followed until the event resolves or has reached a final outcome. Adverse events will be evaluated for severity using NCI CTCAE (Common Toxicity Criteria for Adverse Events) where applicable.

Investigators are required to document all AEs occurring during the study commencing with the date of PAE treatment for patients in the PAE group, and from date of RALRP for the Control group, and including the protocol defined post-treatment follow-up period (21 CFR §312.64[b]), which is defined as 12 months post day of treatment, on the designated CRF pages. AEs that occur following the signature of informed consent but prior to treatment will not be captured. SAEs that occur following the signature of the informed consent but prior to treatment will not be reported.

## **8 Symptom Assessments**

### **8.1 Expanded Prostate Cancer Index Composite (EPIC) Questionnaire**

EPIC is a validated 32-question tool that is self-administered by the patient, and evaluates male urinary function, bowel habits, sexual and hormonal function, and overall satisfaction. A copy of the EPIC questionnaire can be found in Appendix D.

### **8.2 International Index of Erectile Function (IIEF) Questionnaire**

The IIEF is a validated 15-question tool that is self-administered by the patient, and evaluates male sexual function, sexual desire, and intercourse satisfaction. A copy of the IIEF questionnaire can be found in Appendix E.

### **8.3 Pad Weight Test**

Continence will be assessed using the pad weight test. Patients will wear a special pad designed to capture urine leakage for 24 hours. After 24 hours the pad will be weighed to evaluate the amount of urine collected. An increase of <400g indicates continence and an increase of  $\geq$ 400g indicates incontinence.

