### **2.2 Secondary Objectives**

The key secondary objectives are to assess the outcomes listed below and to compare the results for patients who receive PAE and those that do not:

1. Change in hemoglobin on RALRP post operative day (POD) 1 compared to baseline
2. Change in hematocrit on RALRP post operative day (POD) 1 compared to baseline
3. Change in prostate volume between baseline and Visit 3 (6 weeks  $\pm$  2 weeks post PAE) as determined by MRI in patients who receive PAE
4. Blood transfusion requirements during RALRP
5. RALRP duration in minutes
6. Length of hospital stay for RALRP
7. Presence or absence of a complete surgical margin around the entire tumor as determined by histopathology examination post RALRP
8. Biochemical recurrence of prostate cancer as determined by PSA levels post RALRP at 1 year follow up
9. Return to continence post RALRP as assessed by the pad weight test.
10. RALRP related adverse events
11. Erectile function compared to baseline as assessed by the IIEF post RALRP at 1 year follow up.

Additional secondary objectives are to assess outcomes listed below for patients that receive PAE:

12. Change in PSA between baseline and Visit 3 (6 weeks  $\pm$  2 weeks post PAE)
13. PAE related adverse events
14. Histologic changes in the prostate after PAE

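### Sections 8.3 and 9.5.2.8 classify a 24-hour pad gain below 400 g differently, and 9.5.2.8 sets no gram limit for continent, so the proportion continent and the sign-test input are not defined

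*Combined protocol and SAP*

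**What the plan says.** Section 2.2 lists as key secondary objective 9: "Return to continence post RALRP as assessed by the pad weight test". It gives no threshold.

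Section 8.3 describes a 24-hour collection: "After 24 hours the pad will be weighed to evaluate the amount of urine collected". It then gives a two-way rule: "An increase of <400g indicates continence and an increase of" 400 g or more indicates incontinence.

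Section 9.5.2.8 gives a three-way rule. The first class reads "Patients will be classified as being continent if the weight of the pad increase is insignificant". The second reads "mild incontinence if the weight of pad increases by <400 grams over 24 hours". The third, incontinent, starts at 400 g. On the analysis it says "The proportion of continent patients will be calculated for each treatment group at each timepoint", and then "Treatments will be compared using an exact binomial sign test".

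The same section lists the times of the test, beginning "12 days (if urinary catheter is removed), 3 months" and continuing to 6, 9 and 12 months. The Visit 5 list in Section 5.6 contains no pad test, and the grids in Appendices A1 and A2 mark it only under Visits 6 to 9.

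**The concern.** The quantity to be analysed is a yes/no result per patient, and the two sections define that result differently. A patient with a 300 g gain is continent under 8.3. Read plainly, 9.5.2.8 makes the same patient mildly incontinent, and so not continent, unless 300 g is held to be insignificant.

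Section 9.5.2.8 also cannot be applied alone. An insignificant gain is itself a gain below 400 g, so a patient with a few grams fits both of the first two classes. Two programmers working from the same pad weights could report different proportions continent, and each could cite the document.

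Faster return to continence is part of the rationale in Section 1.2. With ten patients per group and no formal sample size calculation (Section 9.2), the descriptive proportions are most of what this outcome can offer.

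**Working it through.** **Step 1. The two rules side by side**

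| 24-hour pad gain | Section 8.3 | Section 9.5.2.8 |
|---|---|---|
| insignificant (no gram value) | continent | continent, but also fits mild incontinence |
| above insignificant, below 400 g | continent | mild incontinence |
| 400 g or more | incontinent | incontinent |

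Only the last row agrees without qualification. Call the middle row the band.

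**Step 2. Effect on one arm's proportion**

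Let b be the number of band patients among n evaluable in an arm. The proportion continent under 9.5.2.8 is lower than under 8.3 by 100 × b/n points. Section 9.2 gives n = 10 per group. Section 6 says withdrawn patients are not replaced, so n = 8 is shown as an assumed smaller number.

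- n = 10: 100 × 1/10 = 10.0 points per band patient
- n = 8: 100 × 1/8 = 12.5 points per band patient

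**Step 3. Effect on the PAE-minus-control difference**

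Shift (9.5.2.8 minus 8.3) = 100 × (b_control/n_control − b_PAE/n_PAE). Every b below is assumed.

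- No band patients: 0
- 2 of 10 in each arm: 20 − 20 = 0, although both proportions fall by 20 points
- 1 of 10 PAE, 0 of 10 control: 0 − 10 = −10; arms swapped, +10
- 3 of 10 PAE, 1 of 10 control: 10 − 30 = −20; arms swapped, +20

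**Step 4. Effect of the missing limit within 9.5.2.8**

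Take ten invented pairs, in grams, listed in pair order. PAE: 0, 2, 5, 10, 20, 40, 80, 150, 300, 450. Control: 3, 15, 30, 60, 90, 120, 200, 350, 420, 600. The limits tried are arbitrary and none is a suggestion. The p values assume a two-sided test.

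| Rule for continent | PAE | Control | Discordant pairs | Sign-test p |
|---|---|---|---|---|
| 8.3, below 400 g | 9/10 | 8/10 | 1 | 1.0 |
| insignificant = below 1 g | 1/10 | 0/10 | 1 | 1.0 |
| insignificant = below 8 g | 3/10 | 1/10 | 2 | 0.5 |
| insignificant = below 50 g | 6/10 | 3/10 | 3 | 0.25 |

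These gains happen to favour PAE; exchanging the labels reverses the direction. They show only that the proportions and the test input both depend on the limit.

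**Step 5. What the sign test can show**

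The documents state neither a significance level nor sidedness for this test. Assume two-sided 0.05. With k discordant pairs all in one direction, p = 2 × 0.5^k.

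- k = 5: p = 0.0625
- k = 6: p = 0.03125

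At least six of ten pairs must be discordant and all one way, so the reported proportions matter more than the test.

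**Step 6. How many results are touched**

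Months 3, 6, 9 and 12 in two arms give 4 × 2 = 8 proportions, or 5 × 2 = 10 if day 12 is kept. Two cautions apply. The text ties the proportions to each timepoint, but that there is one test per timepoint is an inference. Section 9.1 also places the database lock after Visit 7 (month 6), so whether months 9 and 12 will be complete at analysis is unsettled.

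**The case against.** The strongest reply is that much of the difference can be undone. Section 9.1 says categorical variables are reported as a number and percentage per category, and that listings hold all CRF data. If the three classes of 9.5.2.8 are tabulated that way, continent plus mild equals everyone below 400 g, which is the 8.3 proportion. That stands. It does not supply the boundary between continent and mild, and it does not say which yes/no result the sign test uses.

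One might also answer that the statistical section governs, or that mild incontinence is meant to count as continent. Neither is written. The first would still leave a class without a number. The second would reconcile the sections, but it goes against the label and would have to be stated.

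A reader might go further and infer that the ambiguity favours PAE, or that the limit will be picked once pad weights and group are known. The documents support neither. They give no pad-weight data, the shift in Step 3 is symmetric, and a late choice of limit is only a possibility that the missing number leaves open.

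On the 12-day test, a reader might infer that it could never be completed within Visit 5. Sections 4.1 and 5.6 do make that visit the expected time of catheter removal. But Section 5.5 treats discharge with a catheter as conditional and 9.5.2.8 makes the test conditional on removal, so earlier removal is contemplated and the difficulty affects only some patients.

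**Conclusion.** The point holds as a conflict between two stated rules, together with two overlapping classes inside 9.5.2.8. It is more than missing detail, because one label is applied to different patients in the two sections.

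The total effect on the between-group difference is unknown and may be zero. The per-patient figures are arithmetic on the group size; every scenario for the difference rests on assumed counts.

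The reach is limited to one key secondary outcome in a ten-pair proof-of-concept study. The primary outcome, estimated blood loss, does not depend on it, and a reading that the trial's main conclusion is at risk would be wrong. The plan should be corrected because the reported proportions for objective 9 are undefined until it is.

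The omission of the 12-day test from Section 5.6 and both schedules is a separate, smaller inconsistency. A site following the schedule would not collect a measurement that the analysis section expects.

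**What to change.** Reconcile 8.3 and 9.5.2.8 to a single rule, with a numeric gram range for every class and no overlap. The sponsor should choose the limits; the documents do not show which are intended. Fix the rule before outcome data are reviewed, and state which classes count as continent in the sign test. Report all classes at each timepoint so that either grouping can be read from the table. This costs wording only.

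For day 12, choose one of two courses:

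- Drop it from 9.5.2.8, at no cost.
- Add it to 5.6 and to Appendices A1 and A2. This costs one 24-hour collection per patient, and the plan must say how the pad is returned and weighed when the catheter comes out at Visit 5, since that collection ends after the visit.

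A summary of pad gain in grams is optional. It needs no new data if the CRF records the weight, or one added field if it records only the class (the CRF is not shown). It would not resolve the conflict.
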